16.1.5. TEAEs LEADING TO DISCONTINUATION OF STUDY

TEAEs leading to discontinuation from study are those events with an action taken recorded as “permanently discontinued” on the AEs page of the eCRF. Incidence of TEAEs leading to discontinuation from study will be presented by SOC and PT. A listing containing all TEAEs leading to discontinuation from study will also be prepared.

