The first 30 PET scans collected will be reviewed by an independent Data Monitoring Board (DMB). The DMB will assess whether the scans can be evaluated in a manner consistent with methods developed in Phase II (¹⁸F-AV-1451-A05 Exploratory Phase Cohort) as determined by criteria outlined in the Data Monitoring Board Charter. The DMB will have the ability to recommend unblinding the Sponsor to all 30 cases if a prespecified number of scans in the autopsy population have anomalies not present in the early phase studies. Study enrollment will continue during the DMB's review. In the event the Sponsor proceeds with a DMB recommendation for unblinding, the unblinded subjects will be excluded from the Primary Efficacy Cohort (neither the scans nor any autopsies will be used in the primary analyses) or the study may be terminated. If unblinding occurs, it must be completed before the final image read and autopsy methods are specified.

Avid personnel will be blinded to the Primary Efficacy Cohort ¹⁸F-AV-1451 PET images. A single Avid member will perform periodic quality assurance (QA) by reviewing a listing of the PET image header data (not to exceed 20% unless issues identified that warrant additional review). These QA reviews will serve to ensure image quality control processes at the imaging core laboratory are adequately performed. Avid staff performing the PET image data header QA assessment will not be aware of the clinical status for the subjects/images being reviewed. The independent blinded readers and DMB will be blinded to the subject clinical status, PET scan images, and read results. All other Avid personnel will be blinded to the Primary Efficacy Cohort ¹⁸F-AV-1451 read results and pathology data.

Visits and Assessments:

Each subject will have a screening visit, up to two ¹⁸F-AV-1451 PET imaging visits, and a follow-up phone call after each imaging visit. Subjects who come to autopsy during the study period will receive a post-mortem evaluation.

Specific details of assessments that will be performed at each visit are detailed in Section 7.1.

Evaluation of Imaging

Sponsor:	Name of Compound:	Active Ingredient(s):
Avid Radiopharmaceuticals	¹⁸ F-AV-1451	7-(6-[F-18]fluoropyridin-3- yl)-5H-pyrido[4,3-b]indole

¹⁸F-AV-1451 retention on PET images from subjects with valid autopsy data will be interpreted by visual examination as either

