5.5. Removal of Subjects from Trial

Subjects must be removed from the trial if:

- 1. Informed consent is withdrawn; or
- 2. The investigator or the sponsor believes it is in the best interest of the subject to be removed from the trial.

Subjects may be withdrawn from the trial if a serious adverse event occurs. The date and reason for discontinuation should be noted on the eCRF.

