8.3. Safety Analysis

Safety vital signs measurements will be summarized by subject and by evaluation time point. Change from baseline (pre-dose time point) values will be determined and summarized.

Adverse events including injection site reactions will be summarized in terms of number and percentage of subjects experiencing an AE. The summary will be further broken down by system organ class (SOC) and preferred term using Medical Dictionary for Regulatory Activities (MedDRA) terms. Adverse events will also be presented by severity, relationship to treatment and seriousness. All subjects who experience SAEs or who discontinue due to AEs will be summarized.

Discontinuation

All subjects who discontinued participation prior to completing the study will be listed and their discontinuation reasons will be tabulated.

Vital Signs

Changes in vital signs from baseline will be summarized.

8.4. ¹⁸F-AV-1451 Image Analysis

¹⁸F-AV-1451 retention on PET images from subjects with valid autopsy data will be interpreted by visual examination as either

- Neocortical Uptake Not Consistent with an AD Pattern (AD-: no increased neocortical activity in any region or increased activity is isolated to the mesial temporal, anterolateral temporal or frontal region(s);
- Neocortical Uptake Consistent with an AD Pattern (AD+: increased neocortical tracer activity in the posterolateral temporal (PLT), parietal (including precuneus), or occipital region(s)); or
- Neocortical Uptake Consistent with an AD Pattern and with Likelihood of Disease Progression (AD++, which is a subset of AD+ (Neocortical uptake consistent with an AD pattern) where increased tracer activity is found in the parietal (including precuneus) region(s) regardless of uptake elsewhere, or in the frontal region in addition to PLT, occipital, or parietal region(s)).

For the purpose of testing the primary analyses, a scan interpretation will be considered positive (hypothesized to correspond to a B3 neuropathology score in Primary Analysis 1 and an NIA-AA score of high AD pathology in Primary Analysis 2) if the scan is interpreted as at least consistent with an AD pattern (AD+ or AD++). Details of the visual PET image review methods will be provided in the Blinded Read Manual.

Images will also be assessed quantitatively (semi-automated computerized measurement of SUVRs) for exploratory analysis purposes. Details of the analysis methods will be provided in the Quantitative Methodology Document.

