14. EXPOSURE TO ¹⁸F-AV-1451

There is only one scheduled IV bolus injection of ¹⁸F-AV-1451 in this study, unless the subject meets the requirements to undergo a second ¹⁸F-AV-1451 PET (see Section 3.1). For each injection, the net activity administered (mCi) as determined by the PET imaging core laboratory(ies) will be summarized using descriptive statistics for the SAF overall and by most recent neurological disease diagnosis. A similar summary will be presented for the EFF1.

The injection site will be presented in subjects data listing only.

Document:	\\quintiles.net\enterprise\Apps\sasdata\SASa\sas\AVID\18F-AV-1451\Biostatistics\Documentation\SAP\Avid_18F-AV-1451-A16_SAP_Final_v1.0_20180815.docx		
Author:	XXXXXXXXXX	Version Number:	Final, v1.0
		Version Date:	15Aug2018
Template No:	CS_TP_BS016 – Revision 3	Reference:	CS_WI_BS005
Effective Date:	01May2012		

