16.1. ADVERSE EVENTS

AEs will be coded to the SOC and PT using the MedDRA central coding dictionary, version 18.1.

TEAEs are defined as AEs that started or worsened in intensity or frequency on or after an ¹⁸F-AV-1451 injection and up to 48 hours after the ¹⁸F-AV-1451 injection. APPENDIX 1 describes the handling of partial dates and/or times for AEs. In case it is not possible to determine if an AE is treatment emergent or not, the AE will be classified by the worst case; i.e. treatment emergent.

An overall summary of number and percentage of subjects within each of the categories described in the sub-sections below will be provided.

Listings will include all AEs.

Document:	\\quintiles.net\enterprise\Apps\sasdata\SASa\sas\AVID\18F-AV-1451\Biostatistics\Documentation\SAP\Avid_18F-AV-1451-A16_SAP_Final_v1.0_20180815.docx		
Author:	XXXXXXXXXX	Version Number:	Final, v1.0
		Version Date:	15Aug2018
Template No:	CS_TP_BS016 – Revision 3	Reference:	CS_WI_BS005
Effective Date:	01May2012		

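### SAP 16.1.5 selects events leading to study discontinuation by an AE-page action code alone, so it could miss subjects whose recorded reason for leaving is an adverse event

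*SAP*

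**What the plan says.** SAP 16.1.5 defines its table in one sentence, which opens: "TEAEs leading to discontinuation from study are those events with an action taken recorded as". The value it then names is *permanently discontinued*, read from the adverse event page. Counts are shown by system organ class and preferred term, and a listing follows from the same rule. The section does not say whether the thing discontinued is the tracer or the subject's participation.

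On the product, SAP 14 says "There is only one scheduled IV bolus injection of" the tracer, "unless the subject meets the requirements to undergo a second" scan. The protocol synopsis (Visits and Assessments) agrees: "Each subject will have a screening visit, up to two" imaging visits.

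On leaving the trial, Protocol 5.5 allows withdrawal after a serious adverse event and adds: "The date and reason for discontinuation should be noted on the eCRF". SAP 6.3 confirms that date and reason are all that is collected at early termination, and SAP 9 tabulates that reason.

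On reporting, Protocol 8.3 commits to this: "All subjects who experience SAEs or who discontinue due to AEs will be summarized". SAP 16.1 sets the treatment-emergent window: "TEAEs are defined as AEs that started or worsened in intensity or frequency on or after an" injection, up to 48 hours after it.

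**The concern.** The title of the table concerns leaving the study. The selection rule is an action code on the event record, which in the protocol's wording looks like action on the product. For a single bolus these can differ: once the dose is in, there may be nothing left to discontinue, yet the subject can still leave because of an event. The field that records why a subject left is not used.

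At stake is the Protocol 8.3 commitment. A subject could be counted in disposition as having left because of an adverse event while no event for that subject appears in the 16.1.5 table or listing, and the SAP has no step that would detect the gap.

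**Working it through.** No arithmetic applies: the plan gives no rate or expected number of withdrawals due to adverse events. The check compares the sections.

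1. **Label against rule.** In SAP 16.1.3 and 16.1.4 the AE-page field measures what the title says: a fatal outcome for deaths, a serious flag for serious events. In 16.1.5 the title is about the study and the field is an action code whose object is not stated.

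2. **What action taken probably means.** Protocol 7.7 and 7.7.3 list it directly after relationship to investigational product and before outcome. Protocol 7.7 also has a separate instruction for reporting when treatment is stopped because of an event. This points to action on the product. It does not settle the matter, because the eCRF field and its options are not in the documents.

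3. **Where study withdrawal is recorded.** Protocol 5.5 and SAP 6.3 put date and reason on the eCRF as a discontinuation record. SAP 9 uses it; SAP 16.1.5 does not.

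4. **When the code could apply, on the product reading.** The possibilities are an interrupted bolus, a cancelled repeat after an invalid image (SAP 3.1, footnote 1), or a cancelled second scan. A subject whose bolus was completed, who had no further injection in prospect and who was withdrawn because of an event could carry another action code and drop out of the table and listing.

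5. **Scope: treatment-emergent events against all adverse events.** Protocol 8.3 does not restrict discontinuations to treatment-emergent events; SAP 16.1.5 does. The second scan is recommended six to nine months after the first (Protocol 7.1.4). An event between the second consent or dose request and the second injection is classed as trial-emergent (Protocol 7.7.2). Under SAP Appendix 2, a known start more than 48 hours after the first injection and before the second is not treatment-emergent. If such an event made the subject leave, 16.1.5 would exclude it even with the action coded *permanently discontinued*. The same holds for an event starting after 48 hours that is reported only because the investigator attributes it to product or procedure.

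6. **Whether the outputs can be compared.** SAP 5.2 makes the safety set identical to the enrolled set used for disposition. Subject counts from SAP 9 and 16.1.5 therefore rest on the same population and can be reconciled.

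**The case against.** The strongest reply is that SAP 16.1.5 itself equates the action code with discontinuation from the study. If the eCRF option means that the subject was permanently discontinued, the rule does what its title says. The documents do not show the field, so this cannot be excluded. It stands as a limit on the first part of the point. It does not answer the scope difference in step 5, and the SAP would still need to say what is discontinued.

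Second, the injection is not strictly one-time. A second scan and repeats after invalid images are allowed, so the code can apply even on the product reading. This also stands.

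Third, the subjects are not lost. SAP 9 summarizes early discontinuation with reasons, Protocol 8.3 lists all who discontinue, and SAP 16.1 lists all adverse events. What may be missing is the link from the withdrawal to the event term, by system organ class and preferred term.

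A reader might go further and infer that the table would be nearly empty because of this rule, or that almost every relevant discontinuation would be missed. The documents do not support that. They give no count of such withdrawals. The table is limited to events within 48 hours of an injection, and adverse event reporting ends with the follow-up call (Protocol 7.1.2), so few entries are likely under any definition. Sparseness cannot be blamed on the action code. Nor must disposition and 16.1.5 counts agree as written: disposition covers leaving at any time, and SAP 9 does not list its reason categories.

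**Conclusion.** The point holds in a limited form. SAP 16.1.5 uses one AE-page action code for a table about leaving the study and ignores the recorded reason for leaving. If the code refers to the tracer, which the protocol wording suggests but does not confirm, a subject withdrawn because of an event after a completed bolus could be missing from the table by event term and from its listing, while still counted in disposition. Independently of that assumption, the restriction to treatment-emergent events is narrower than Protocol 8.3 and leaves out, for example, a trial-emergent event before a planned second injection.

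The number affected is unknown and probably small. Only a descriptive safety output is touched; no efficacy result, error rate or sample size depends on it. The change is still worth making, because it bears on an explicit protocol commitment and the proposed rule is correct whichever meaning the field has.

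**What to change.** Replace the defining sentence of SAP 16.1.5. The set should be all adverse events in subjects whose eCRF study-discontinuation reason is an adverse event, matched to the event record by subject and date, plus any adverse event with action *permanently discontinued*. Flag which are treatment-emergent, and reconcile the number of subjects with the SAP Section 9 disposition table.

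Because SAP 6.3 describes only a date and a reason at early termination, some matches may be ambiguous or absent. List those subjects as unmatched, so that the reconciliation shows them. If the eCRF instructions establish what *permanently discontinued* refers to, state it in the same place.

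The cost is one SAP sentence and a merge of data already collected.

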16.2. LABORATORY EVALUATIONS

Not applicable.

16.3. ECG EVALUATIONS

Not applicable.

16.4. VITAL SIGNS

Vital sign measurements (pulse rate, respiratory rate, and blood pressure) will be taken in the supine position at screening, immediately prior to the ¹⁸F-AV-1451 injection, and after completion of the imaging prior to discharge.

The change in vital sign measurements from baseline to completion of imaging prior to discharge will be computed as the value collected after the completion of the imaging prior to discharge minus the baseline value. Observed and change from baseline values will be summarized through use of descriptive statistics for the each ¹⁸F-AV-1451 injection.

Incidence of potentially clinically significant abnormal values will also be provided for each ¹⁸F-AV-1451 injection and a listing of subjects with potentially clinically significant abnormal values will be prepared.

16.4.1. POTENTIALLY CLINICALLY SIGNIFICANT ABNORMAL VITAL SIGNS CRITERIA

Potentially clinically significant abnormal vital sign measurements will be identified in accordance with the following criteria:

Document:	\\quintiles.net\enterprise\Apps\sasdata\SASa\sas\AVID\18F-AV-1451\Biostatistics\Documentation\SAP\Avid_18F-AV-1451-A16_SAP_Final_v1.0_20180815.docx		
Author:	XXXXXXXXXX	Version Number:	Final, v1.0
		Version Date:	15Aug2018
Template No:	CS_TP_BS016 – Revision 3	Reference:	CS_WI_BS005
Effective Date:	01May2012		

Table 4 Potentially Clinically Significant Abnormal Vital Signs Criteria

Variable	Unit	Low	High
SBP	mmHg	≤ 90 mmHg AND change from baseline ≤ -20 mmHg	≥ 180 mmHg AND change from baseline ≥ 20 mmHg
DBP	mmHg	≤ 50 mmHg AND change from baseline ≤ -15 mmHg	≥ 105 mmHg AND change from baseline ≥ 15 mmHg
Pulse rate	bpm	≤ 50 bpm	≥ 110 bpm AND change from baseline ≥ 20 bpm
Respiratory rate	breaths/ min	≤ 10 breaths/min	NA

16.5. PHYSICAL AND NEUROLOGICAL EXAMINATIONS

A brief medical examination will be conducted by a medically qualified study team member at the screening visit. Clinically significant changes from screening will be recorded as AEs.

A brief neurological examination will also be performed by a medically qualified study team member at the screening visit to evaluate cranial nerves, gait, sensory, motor function, coordination, and tendon reflexes. Clinically significant changes from screening will be recorded as AEs.

Incidence of physical and neurological abnormalities at screening will be provided.

Document: \\quintiles.net\enterprise\Apps\sasdata\SASa\sas\AVID\18F-AV-1451\Biostatistics\Documentation\SAP\Avid_18F-AV-1451-A16_SAP_Final_v1.0_20180815.docx

Author: XXXXXXXXXX

Version Number: Final, v1.0

Version Date: 15Aug2018

Template No: CS_TP_BS016 – Revision 3

Reference: CS_WI_BS005

Effective Date: 01May2012

Copyright © 2012 Quintiles Transnational Corp. All rights reserved.

The contents of this document are confidential and proprietary to Quintiles Transnational Corp. Unauthorized use, disclosure or reproduction is strictly prohibited.

All data collected on the eCRF will be presented in data listings. The listings will be ordered by the following (unless otherwise indicated in the shells): most recent neurological disease diagnosis, subject number, date, and time (where applicable).

Document: \\quintiles.net\enterprise\Apps\sasdata\SASa\sas\AVID\18F-AV-1451\Biostatistics\Documentation\SAP\Avid_18F-AV-1451-A16_SAP_Final_v1.0_20180815.docx

Author: XXXXXXXXXX

Version Number: Final, v1.0

Version Date: 15Aug2018

Template No: CS_TP_BS016 – Revision 3

Reference: CS_WI_BS005

Effective Date: 01May2012

Copyright © 2012 Quintiles Transnational Corp. All rights reserved.

The contents of this document are confidential and proprietary to Quintiles Transnational Corp. Unauthorized use, disclosure or reproduction is strictly prohibited.

APPENDIX 2. PARTIAL DATE AND/OR TIME CONVENTIONS

ALGORITHM FOR PRIOR / CONCOMITANT MEDICATIONS

START DATE	STOP DATE	ACTION
Known/ Partial/ Missing	Known/ Ongoing	If stop date < ¹⁸ F-AV-1451 injection date, assign as prior If stop date ≥ ¹⁸ F-AV-1451 injection date or medication is ongoing, assign as concomitant.
	Partial	If known components of stop date show that: 
 • Stop date < ¹⁸F-AV-1451 injection date, assign as prior • Stop date ≥ ¹⁸F-AV-1451 injection date, assign as concomitant.
	Missing	Assign as concomitant

ALGORITHM FOR TREATMENT EMERGENCE OF ADVERSE EVENTS

START DATE/TIME	STOP DATE/TIME	ACTION
Known	Known, Partial, Missing	If start date/time < ¹⁸ F-AV-1451 injection date/time, then not TEAE If ¹⁸ F-AV-1451 injection date/time ≤ start date/time ≤ ¹⁸ F-AV-1451 injection date/time + 48 hours, then TEAE If start date/time > ¹⁸ F-AV-1451 injection date/time + 48 hours, then not TEAE
Partial, but known components show that it cannot be on or after ¹⁸ F-AV-1451 injection date/time and within 48 hours post-injection	Known, Partial, Missing	Not TEAE
Partial and known components show that it could be on or after ¹⁸ F-AV-1451 injection date/time and within 48 hours post-injection	Known, Partial, Missing	Assumed TEAE
Missing	Known	If stop date/time < ¹⁸ F-AV-1451 injection date/time, then not TEAE If stop date/time ≥ ¹⁸ F-AV-1451 injection date/time, then TEAE

Document: \\quintiles.net\enterprise\Apps\sasdata\SASa\sas\AVID\18F-AV-1451\Biostatistics\Documentation\SAP\Avid_18F-AV-1451-A16_SAP_Final_v1.0_20180815.docx

Author: XXXXXXXXXX

Version Number: Final, v1.0

Version Date: 15Aug2018

Reference: CS_WI_BS005

Template No: CS_TP_BS016 – Revision 3

Effective Date: 01May2012

Copyright © 2012 Quintiles Transnational Corp. All rights reserved.

The contents of this document are confidential and proprietary to Quintiles Transnational Corp. Unauthorized use, disclosure or reproduction is strictly prohibited.

START DATE/TIME	STOP DATE/TIME	ACTION
	Partial	If known components of stop date/time show that: 
 • Stop date/time < ¹⁸F-AV-1451 injection date/time, then not TEAE • Stop date/time ≥ ¹⁸F-AV-1451 injection date/time, then TEAE
	Missing	Assumed TEAE

Document: \\quintiles.net\enterprise\Apps\sasdata\SASa\sas\AVID\18F-AV-1451\Biostatistics\Documentation\SAP\Avid_18F-AV-1451-A16_SAP_Final_v1.0_20180815.docx

Author: XXXXXXXXXX Version Number: Final, v1.0
 Version Date: 15Aug2018

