7.7.2. Adverse Event Definitions

Adverse Events

For reporting purposes, Avid will distinguish among pre-existing conditions, treatment emergent adverse events and trial-emergent adverse events. Pre-existing conditions (i.e., undesirable experiences, signs or symptoms that begin prior to the Screening Visit) will be recorded on the medical history and/or physical exam eCRF pages. Signs and symptoms that are believed to be due to the pre-existing condition (started prior to dose of investigational product) do not have to be recorded in the AEs section of the eCRF, unless there is an increase in frequency or severity. Additionally, signs or symptoms or changes in pre-existing conditions that occur outside the trial-defined adverse event reporting will be recorded in medical history.

An adverse event is any untoward medical occurrence associated with the use of a drug in humans, whether or not considered drug related. For the purposes of this study, untoward medical occurrences will be considered associated with the use of ¹⁸F-AV-1451, and thus be reported as treatment-emergent adverse events, if they occur within 48 hours after ¹⁸F-AV-1451 administration.

In the context of this study, adverse experiences including hospitalizations, medical complications and death are expected, since terminal illness is a requirement for entry into the study. Thus, if the investigator becomes aware of such events that occur after administration of the drug but outside the 48 hour reporting window, these will only be reported as adverse events if the investigator believes they are attributable to the investigational product or protocol procedure.

In order to capture possible adverse effects of trial participation, any untoward medical occurrences occurring after the informed consent until the administration of ¹⁸F-AV-1451 will be recorded in the CRF for reporting as trial-emergent adverse events. If the subject consents to a second ¹⁸F-AV-1451 PET scan, trial-emergent adverse events will be collected in a similar period, from either date of additional consent (if applicable) or the date the dose request for the second scan is submitted to Avid, up to the second administration of ¹⁸F-AV-1451.

Serious Adverse Event (SAE)

An SAE is an AE that results in one of the following outcomes or constitutes one of the following events:

- Death;

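### SAP Appendix 2 has no branch for worsening, so it can class as not treatment-emergent an adverse event that SAP 16.1 defines as treatment-emergent

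*SAP*

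**What the plan says.** - **Definition (SAP 16.1).** TEAEs are events that "started or worsened in intensity or frequency on or after an" injection, with the window closing 48 hours later. Where emergence cannot be determined, "the AE will be classified by the worst case; i.e. treatment emergent".
- **Algorithm (SAP Appendix 2, treatment emergence table).** The first row covers fully known start dates/times. If the start is before the "injection date/time, then not TEAE", whatever the stop date. The second row, headed "Partial, but known components show that it cannot be on or after" injection and within the 48 hours, also gives not TEAE. Later rows cover ambiguous or missing starts and mostly default to TEAE. No row uses a date of worsening or a change in intensity or frequency.
- **Recording (Protocol 7.7.2).** Signs and symptoms of pre-existing conditions "do not have to be recorded in the AEs section of the eCRF, unless there is an increase in frequency or severity". Untoward events between consent and injection are recorded as trial-emergent adverse events. A similar collection period applies before a second injection.
- **Cross-reference.** SAP 16.1 sends the reader to Appendix 1 for partial adverse event dates. Appendix 1 holds output conventions. The date rules are in Appendix 2, as SAP 7.3 correctly says.

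**The concern.** The definition has two limbs, onset and worsening, and the algorithm carries out only the first. A programmer who follows Appendix 2 drops the second limb whenever onset is established as earlier than injection. On this point the discrepancy runs one way: the algorithm can lose worsening events but cannot add any.

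This also runs against the SAP's otherwise cautious conventions. Missing severity is counted as severe, missing relationship as related, and an event with no dates at all as treatment-emergent. Yet an event with a well-documented earlier onset and a documented post-dose worsening is excluded. At stake is whether the main post-dose safety tables in SAP 16.1.1 show what the SAP says they show.

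**Working it through.** The plan gives no figure on this point, so the check is a comparison of rules. Take one event that begins before injection, is still present at injection, and worsens within 48 hours after it. Under SAP 16.1 it is a TEAE. The branches of Appendix 2 give:

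| Recorded start | Appendix 2 | SAP 16.1 | Agree? |
|---|---|---|---|
| Known, before injection | Not TEAE, whatever the stop date | TEAE | No |
| Partial, certainly before injection | Not TEAE | TEAE | No |
| Partial, could fall in the window | Assumed TEAE | TEAE | Yes |
| Missing, stop on or after injection | TEAE | TEAE | Yes |
| Missing, stop also missing | Assumed TEAE | TEAE | Yes |

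The remaining branch, a missing start with a stop before injection, gives not TEAE. It causes no conflict, because an event that has ended cannot worsen. The conflict is therefore confined to events whose start is known, or shown by partial dates, to precede injection.

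**Does the worst-case rule rescue them?** No. That rule applies only when emergence cannot be determined, and these two rows give a definite answer.

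**Can such records exist?** Yes.
- Protocol 7.7.2 records events from consent to injection. Protocol 7.1.1 prefers screening within 45 days before imaging, so an event may already have its own record, with a pre-injection start, on the day of dosing.
- The same can happen before a second injection, since SAP 16.1 refers to any injection and not only the first.
- Neither document says that a later worsening must be opened as a new record dated at the worsening.

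**Which outputs are affected?**
- SAP 16.1.1 restricts its incidence tables, and their breakdowns by severity and by relationship to drug and procedures, to TEAEs.
- SAP 16.1.3 (fatal outcome) and 16.1.4 (serious events) define their events from the eCRF outcome and seriousness fields, without a TEAE restriction.
- SAP 16.1 lists all adverse events.
- Efficacy uses none of these data.

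**The case against.** The strongest reply is that the recording rules already solve the problem. Under Protocol 7.7.2, a pre-existing condition sits in medical history and reaches the adverse event page when it increases in frequency or severity, so the worsening itself creates the record. Protocol 7.2 (Physical Examination) ties clinically significant changes from screening to the study period in which they occur. The fields named in Protocol 7.7 and 7.7.3 include start and stop dates and severity but no date of worsening, so a new record is the natural way to capture one. SAP 16.1.1.1 expects the same event to be reported more than once. If the new record starts on the day of worsening, Appendix 2 classifies it correctly.

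Much of this stands for pre-existing conditions, although even there the start date to enter is not stated. It does not cover an event first recorded between consent and injection, which has an adverse event record before any worsening occurs.

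A second reply is that Appendix 2 is titled as a partial-date convention, and that SAP 7.3 and 16.1 invoke it only for missing or partial dates. The definition in 16.1 would then govern. But the first row of the table explicitly deals with known start dates and gives a definite result, so the two texts still need to agree.

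**Conclusion.** The contradiction between SAP 16.1 and Appendix 2 is real. It leads to omission from the TEAE tables under three conditions together: the start is established as before injection, the worsening falls within 48 hours after it, and the worsening stays under the existing record and start date. The clearest case is a trial-emergent event under Protocol 7.7.2.

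A reader might infer more, and the documents do not support it:
- **That TEAEs will be undercounted.** They could be. If sites opened a new record dated at the worsening, nothing is lost, and the documents do not settle which practice was used.
- **That every event with an earlier onset is lost.** Events with ambiguous starts, or with missing starts and no stop before injection, are classed as TEAEs.
- **That worsening events vanish from the safety report.** A serious or fatal one stays in its own table, and every event is listed.
- **That the undercount can be expressed as a rate.** The documents give no count of new-onset or worsening events, so any percentage would rest on invented inputs.

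No primary or secondary efficacy conclusion is touched. The point is an internal inconsistency in the safety rules, cheap to remove.

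**What to change.** Make Appendix 2 agree with SAP 16.1 in one of two ways.

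1. State that each worsening is handled as a separate adverse event record whose start date/time is that of the worsening. The existing algorithm then applies unchanged. This is the more practical route if no worsening date was collected.
2. If a worsening date or grade change is captured, add a row: a start before injection, with an increase in intensity or frequency from injection to 48 hours after either injection, is a TEAE. Where the timing of the worsening cannot be determined, treat it as a TEAE under the worst-case rule in 16.1.

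Also change the pointer in 16.1 from Appendix 1 to Appendix 2.

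The cost is one sentence or one row plus a cross-reference, with some programming for the second route. The TEAE count may rise slightly, and the undeterminable-timing default in the second route could count some events that did not worsen in the window.
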